## **7. Risks and Discomforts**

We believe that the risks to participation for both physicians and patients are no more than minimal for several reasons. First, the interventions aim to emphasize guideline-recommended treatments for patients with persistently elevated blood pressure. Second, all treatment decisions will ultimately be made by licensed primary care physicians. Finally, the intervention is physician-focused and delivered through interventions that use information already available to physicians that is also guideline concordant and intended to reduce disparities in care. We believe there is no more than minimal risk

involved to the physician subjects, as the physicians will simply be given tools to alter their behaviors towards guideline recommended care. All medical decisions are ultimately made by the physician. This trial will not interfere with the ordinary workings of the primary care practices.

There is a small risk associated with altering hypertension medication prescribing, including hypotension, bradycardia, allergic reactions, and other adverse effects. However, in prior trials that increase intensification of blood pressure regimens, the risks have been similar in intervention and control arms. We believe the potential risks of treatment intensification as part of this trial are the same, or less than what is encountered during routine, guideline-concordant hypertension care, given the focus on patients with persistently elevated blood pressure. Final prescribing decisions will always be at the discretion of the patient's PCP.

Another potential small risk to patients will be privacy of health information. We will minimize the risk to privacy by taking appropriate steps to limit access to data to study investigators. Clinical data on the care for patients will be retrieved from the electronic medical records.

## **8. Benefits**

This study is designed to improve electronic health record prescribing tools for providers caring for adult patients with uncontrolled hypertension. Potential benefits for participants in this study include improved decision support tools and guideline-concordant prescribing. Thus, the research could have both immediate benefits for physicians by increasing hypertension awareness and treatment knowledge, as well as for their patients who might benefit from improved blood pressure control. We will also evaluate implementation of the interventions to allow for future scalability.

Additionally, the subjects and society may benefit in the future from accumulated knowledge that originates from this research. We will also produce several EHR tool deliverables for this work for the public, researchers, and policymakers, which will be shared as generalized knowledge.

## **9. Statistical Analysis**

### 9.1. Statistical hypothesis

We hypothesize that the intervention will lower mean systolic blood pressure to a larger degree than usual care. The null hypothesis will be no difference between patients identified as eligible in the intervention arm and usual care. All analyses will use intention-to-treat principles.

### 9.2. Sample size determination

We powered the study to detect a 5.0 mmHg mean change in SBP between the intervention arm and control arm from randomization through 12 months, assuming a standard deviation (SD) of 13.5, an alpha threshold of 0.05, and an intra-cluster correlation (ICC) of 0.1. With these assumptions, we estimated that at least 24 eligible primary care clinics including 537 providers and 49395 patients that were identified as eligible for inclusion in the analysis will provide >80% power to detect differences in our primary outcome. The 5.0 mmHg mean change was chosen as this is considered to a clinically meaningful change in SBP and was observed in prior systematic reviews of interventions in hypertension. This estimate also accounts for regression to the mean and includes SDs that were derived from our prior work and Advocate feasibility data.

### 9.3. Analyses of endpoints

Descriptive statistics will be calculated for all variables and presented overall and by group using mean + SD for continuous variables, as well as counts or percentages for categorical variables. Comparisons will be made between groups for all outcomes using absolute standardized differences. The unit of analysis is at the patient-level.

For the primary outcome, we will use generalized estimating equations (GEE) to adjust for the cluster design with an identity link function and normally-distributed errors. If >10% of data is missing, we will use multiple imputation for our study outcomes, as we have done in prior research. We will test the robustness of this approach with sensitivity analyses that use alternative methods of handling missing data. For baseline characteristics between arms with a standardized difference >0.1, we will repeat our analyses after adjusting for these covariates. We will also conduct analyses by racial/ethnic subgroup. In secondary analyses, we will also use longitudinal modeling to account for multiple SBP values over follow-up.

For secondary outcomes, we hypothesize that the intervention will lead to more patients with well-controlled blood pressures, higher rates of treatment intensification and guideline concordance. The null hypotheses will be no difference between the intervention arm and usual care. For these outcomes, we will use GEE with an identity link and normally-distributed errors for continuous variables and with a log-link function and Poisson-distributed errors for categorical variables. For outcomes that are non-normal, we will use GEE with a log-link function and Poisson-distributed errors, as in our prior work. For all primary and secondary outcomes, the study analysts and investigators will be blinded to treatment allocation until after the analyses are complete. We will also evaluate other implementation outcomes, including clinical outcomes past the initial 12 month follow-up, until 24 months (i.e., the end of the trial), to explore durability of treatment effects.

De-identified qualitative interview transcripts (interviews previously conducted under the IRB approval of Advocate Aurora Health) will be analyzed using immersion-crystallization methods using Dedoose qualitative software (SocioCultural Research Consultants, LLC). In this approach, we immerse ourselves in the collected data and then articulate the salient themes during the crystallization process. We will continue this approach of cycles of concentrated textual review until all data are examined, and meaningful patterns emerge from the data. Collected data will be used to describe and understand both patient and providers perspectives on hypertension management.

Because this is a randomized trial, our primary analyses are planned as unadjusted; however, if there are strong patient-level predictors of the outcomes not balanced by stratified randomization, we will adjust for these in the primary analyses.

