#### *6.2.4 Post-visit interventions*

We will streamline patient-subjects' access to the online patient portal by including information about the patient portal in the patients' after-visit summary and enabling providers to order nurse blood pressure check visits. Advocate has 24/7 online appointment scheduling capabilities that can be leveraged.

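### Section 9.3 ties multiple imputation to an undefined 10% missing rate and names no primary method at or below it, leaving by default a comparison of patients who happen to have a follow-up reading

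*Combined protocol and SAP*

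**What the plan says.** All of the missing-data plan is in Section 9.3.

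- **Trigger.** "If >10% of data is missing, we will use multiple imputation for our study outcomes". The section does not say whether the rate is that of the primary outcome, of each outcome or of all variables, or whether it is pooled or by arm. Nothing is stated for 10% or less.
- **Sensitivity analyses.** The next sentence reads: "We will test the robustness of this approach with sensitivity analyses that use alternative methods of handling missing data". The methods are not named.
- **Primary model.** "we will use generalized estimating equations (GEE) to adjust for the cluster design with an identity link function and normally-distributed errors".
- **Covariates.** At the end of the section, "our primary analyses are planned as unadjusted", with an exception: "if there are strong patient-level predictors of the outcomes not balanced by stratified randomization, we will adjust for these in the primary analyses". Separately, "For baseline characteristics between arms with a standardized difference >0.1, we will repeat our analyses after adjusting for these covariates".
- **Repeated readings.** A longitudinal model of SBP over follow-up is planned as a secondary analysis.

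Other sections describe how a reading comes to exist. The primary endpoint uses values recorded in the EHR (Section 6.5), and the trial has no visits of its own (Section 6.3). The Background (Section 1) says that minority patients return to care less often than white patients. The intervention includes a dashboard showing the next appointment (Section 6.2.2) and post-visit tools, among them "enabling providers to order nurse blood pressure check visits" (Section 6.2.4). Section 2 hypothesises better post-visit follow-up in the intervention arm.

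**The concern.** The primary missing-data method is not fixed in advance. It depends on a rate known only once the data are in, and because that rate is undefined, two analysts could disagree on whether the cut was crossed.

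At or below the cut, the only specified analysis is the GEE. Run on available outcomes with no imputation, it compares patients who have a 12-month reading. An unadjusted two-arm comparison of this kind is unbiased if, within each arm, having a reading is unrelated to the change in SBP. The trial gives reasons to doubt that. A reading needs a return visit, return differs by race/ethnicity on the plan's own account, and the intervention is meant to increase follow-up contact. Selection by return would pass directly into the arm difference.

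A pooled cut can also hide an imbalance between arms: with equal arms, 5% and 15% missing average 10% and do not trigger imputation.

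**Working it through.** **Step 1. Reproduce the plan's power, to get a standard error.** Inputs from Section 9.2: difference 5.0 mmHg, SD 13.5, ICC 0.1, alpha 0.05 (two-sided assumed), 24 clinics, 49395 patients. Equal allocation is from Section 5.2.

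- Mean cluster size: 49395/24 = 2058.1.
- Design effect: 1 + (2058.1 − 1) × 0.1 = 206.7.
- Effective n per arm: 49395/206.7/2 = 119.5.
- SE of the difference: 13.5 × √(2/119.5) = 1.747 mmHg.
- Power, normal approximation: 81.7%, which agrees with the stated figure of over 80%. With a t reference on 22 df it is 78.1%. The plan states no reference distribution, and this point does not depend on the choice.

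**Step 2. Precision.** If 10% of patients are lost evenly, power is 81.6% against 81.7%. With clusters this large, the loss of patients hardly matters. The issue is bias.

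**Step 3. Bias of a complete-case comparison.** Let f be the missing share in an arm, and g the mean SBP change in patients without a reading minus that in patients with one. The true arm mean is the observed mean plus f × g. For intervention (I) minus control (C):

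bias = f_C × g_C − f_I × g_I

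The documents give neither f nor g, so every row is an assumption. All have 10% missing overall, so a pooled rule would not trigger imputation.

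| f_I | f_C | g_I (mmHg) | g_C (mmHg) | Bias (mmHg) | Share of 5.0 target |
|---|---|---|---|---|---|
| 10% | 10% | 5 | 5 | 0 | 0 |
| 10% | 10% | 10 | 10 | 0 | 0 |
| 10% | 10% | 5 | 0 | −0.5 | 10% |
| 10% | 10% | 10 | 0 | −1.0 | 20% |
| 5% | 15% | 5 | 5 | +0.5 | 10% |
| 5% | 15% | 10 | 10 | +1.0 | 20% |

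For row five: 0.15 × 5 − 0.05 × 5 = 0.75 − 0.25 = 0.5. A benefit is a negative difference, so a positive bias runs towards no effect. Reversing the sign of g reverses the direction.

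**Step 4. What 0.5 mmHg does.** It is 0.5/1.747 = 29% of the SE.

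| Bias (mmHg) | Power if towards the null, normal | Power if towards the null, t(22) | Type I error, t(22), no true effect |
|---|---|---|---|
| 0 | 81.7% | 78.1% | 5.0% |
| 0.25 | 77.6% | 73.9% | 5.2% |
| 0.5 | 73.1% | 69.2% | 5.9% |

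The 0.25 row corresponds to a 5-point difference in missing share and a 2.5 to 1 smaller imbalance is not needed to reach it: 0.05 × 5 = 0.25, with the same gap in both arms.

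**The case against.** The strongest case on the other side has five parts.

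1. **A robustness check is promised.** A reader might infer that none exists at 10% or less, taking the approach whose robustness is tested to be imputation alone. The text does not settle this: it may equally mean the whole threshold rule, in which case a check exists on both sides of the cut. What stands is that the methods are unnamed and their scope is unclear. A sensitivity analysis would also not settle which estimate is primary.
2. **Complete-case analysis is not stated.** It is inferred from silence. Nor is the analysis always unadjusted: imbalanced strong predictors enter the primary analysis, and an adjusted repeat and a longitudinal model are planned. This stands, but none of these is presented as a missing-data method.
3. **It would be too strong to say that readings must be missing completely at random.** The requirement applies within each arm, so missing rates may differ between arms without bias if the gap is zero in both.
4. **The rule is prespecified.** It depends on the missing rate and not on the treatment effect, and Section 9.3 keeps analysts and investigators blinded to allocation until the analyses are complete. A reader might infer a choice driven by the result; the documents do not support that. The undefined rate and the unspecified branch remain.
5. **The affected branch may not arise.** With no study visits, missingness may well exceed 10%, and then imputation already applies. Nor does imputation help where return depends on blood pressure that was never recorded. Both are right and limit the gain.

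**Conclusion.** The point holds as a cheap improvement, not as a demonstrated bias. Section 9.3 leaves the 10% rate undefined, names no primary handling at or below it, and leaves the sensitivity analyses unnamed and of uncertain reach. By default the primary result in that branch is a comparison of patients with a follow-up reading, under an assumption that the plan's own account of return to care makes doubtful.

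The size rests on assumed inputs. With 5% v 15% missing and a 5 mmHg gap in both arms, the bias is about 0.5 mmHg. Over the values shown in the working it runs from 0 to 1.0 mmHg in either direction. It is zero if missing shares and gaps are equal in both arms. If more than 10% is missing, the choice of method does not change. The documents do not support saying that the plan has no robustness check, or that it commits to complete-case analysis.

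**What to change.** Amend Section 9.3 as follows.

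- Delete the 10% trigger. State that primary SBP is analysed with multiple imputation whatever the proportion missing.
- Specify the imputation model: allow for clinic clustering, and include arm, index SBP, available follow-up SBP readings and race/ethnicity.
- Name the sensitivity analyses and run them in every case: the complete-case GEE, and a delta-adjusted analysis that lets readings be missing not at random.
- Report the number and share of missing readings by arm.

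The cost is SAP wording and a small amount of extra analysis work, with no new data and no added patients. Imputation removes only the part of the bias explained by variables in the model. Patients who never return have no follow-up readings to contribute, which is why the delta-adjusted analysis belongs in the plan.

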### **6.5 Study endpoints**

The trial will be completed 24 months after trial launch. At the end of the study period, data will be extracted retrospectively from electronic health records; the primary analysis will be on patients who visited one of the 24 clinics during the study period and who meet the inclusion criteria.

Primary:

- Change in systolic blood pressure from patient identification (i.e., the most recent encounter that identified the patient as eligible) through 12-month follow-up, using values recorded in the EHR

Secondary:

- Percentage of patients with well-controlled blood pressure (<140/88mmHg) or <130/80 mmHg for those with comorbid conditions defined by clinical guidelines at 12 months follow-up, using values in the EHR
- Percentage of patients with intensification of medication in the 12-month follow-up period, defined by addition of therapy or increasing dose
- Percentage of patients with guideline-concordant medications ordered in the 12-month follow-up period
- Change in the gap in systolic blood pressure between each of Black and Hispanic/Latino patients and non-Hispanic White patients from the last encounter before identification through 12 months after, using values in the EHR
- Change in diastolic blood pressure from the encounter before identification through 12 months after, using values recorded in the EHR

Exploratory:

- Frequency of viewing the dashboard, SmartSet order set, documentation choices, and acknowledgement reasons
- Intervention fidelity: BPAs (alerts) firing as intended

Clinical encounters, using number of office visits, telephone calls and patient portal interactions between AAH primary care providers and patients during the 12-month follow-up period. These outcomes will also be measured in the remainder of the follow-up period until the end of administrative censoring at the end of the 2-year trial.

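### Section 9.3 sends any outcome called non-normal to a log-link Poisson GEE, a model unsuited to the signed blood pressure changes among the secondary endpoints

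*Combined protocol and SAP*

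**What the plan says.** Section 9.3 has a paragraph for the primary outcome and another for the secondary outcomes.

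- Primary outcome (SBP change): a GEE to "adjust for the cluster design with an identity link function and normally-distributed errors". That paragraph contains no fallback for non-normality.
- Secondary outcomes, continuous: "we will use GEE with an identity link and normally-distributed errors for continuous variables".
- Secondary outcomes, categorical: a GEE "with a log-link function and Poisson-distributed errors for categorical variables".
- Then, in the secondary paragraph and without further limit: "For outcomes that are non-normal, we will use GEE with a log-link function and Poisson-distributed errors, as in our prior work".

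Section 9.3 also states "The unit of analysis is at the patient-level". It names no test or threshold for non-normality.

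Section 6.5 lists five secondary endpoints. Three are percentages of patients: blood pressure control, treatment intensification, and guideline-concordant medication. The other two are "Change in diastolic blood pressure from the encounter before identification through 12 months after, using values recorded in the EHR" and "Change in the gap in systolic blood pressure between each of Black and Hispanic/Latino patients and non-Hispanic White patients". Counts of office visits, telephone calls and portal contacts appear under the exploratory endpoints.

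**The concern.** The default for a continuous secondary outcome is suitable. The difficulty is the sentence that can override it. A change in blood pressure is negative when pressure falls and positive when it rises. A log link requires a positive mean, and a Poisson variance equal to the mean has no meaning for a score centred at or below zero. The plan expects pressure to fall, at least for SBP: "We hypothesize that the intervention will lower mean systolic blood pressure to a larger degree than usual care".

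If DBP change or SBP change is judged non-normal, the prespecified analysis either cannot be fitted or reports a different quantity: a ratio of mean changes in place of a difference in mmHg. For the gap endpoint, which is defined as a difference between groups, a ratio does not answer the stated question. Because non-normal is undefined, the effect measure for these endpoints would be settled by an unspecified judgement on the outcome data.

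**Working it through.** **The plan's own figure.** The plan gives no number on this point. Its only related figure is power above 80% for the primary outcome (Section 9.2: 24 clinics, 49395 patients, SD 13.5, ICC 0.1, difference 5.0 mmHg). Mean clinic size is 49395/24 = 2058.1, the design effect is 1 + 2057.1 × 0.1 = 206.7, and the effective number per arm is 49395/206.7/2 = 119.5. Power at two-sided 0.05 is then 81.7% by the normal approximation, which agrees with the plan, and 78.1% with a t reference on 22 df. The point does not depend on this figure, but the difference shows that the number of clinics matters for inference.

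**Which secondary endpoints the fallback can alter (Sections 6.5 and 9.3).**

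- Three percentages: already log-link Poisson under the categorical rule, so no change.
- DBP change: identity link by default, log-link Poisson if called non-normal.
- SBP gap: a contrast between groups, not a value held by each patient. The plan does not spell out its model. I take it as a race/ethnicity-by-arm term in a patient-level model of SBP change, so the fallback reaches it through that change.

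**Why the log link fails.** With arm as the only covariate and an independence working structure, the estimating equations set each fitted arm mean equal to the observed arm mean. The control-arm equation is exp(b0) = observed control mean, which has no real solution if that mean is zero or negative.

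**Share of negative values.** The documents give no mean, SD or sign convention for these changes. For follow-up minus baseline, assumed normal, the share is Φ(−mean/SD):

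| Assumed mean change (mmHg) | SD 8 | SD 13.5 |
|---|---|---|
| 0 | 50% | 50% |
| −2 | 60% | 56% |
| −5 | 73% | 64% |
| −10 | 89% | 77% |

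**Simulated fits (assumed inputs).** 24 clinics of 200 patients, half per arm, SD 10, ICC 0.02, one data set per row. Independence and exchangeable structures gave the same results.

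| Target means (control, intervention) | Realised means | Negative values | Identity-link difference (SE), mmHg | Log-link Poisson |
|---|---|---|---|---|
| −3, −5 | −2.67, −5.15 | 65% | −2.48 (0.51) | stopped, invalid weights |
| 0, −2 | −0.25, −2.84 | 56% | −2.58 (0.62) | stopped, invalid weights |
| −8, −13 | −8.78, −12.75 | 85% | −3.96 (0.59) | stopped, invalid weights |
| 3, 5 (sign reversed) | 3.33, 4.90 | 33% | 1.57 (0.71) | ratio exp(0.387) = 1.47 |
| 8, 13 (sign reversed) | 8.05, 12.40 | 16% | 4.35 (0.58) | ratio exp(0.432) = 1.54 |

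In the last two rows the ratios are close, 1.47 and 1.54, while the differences in mmHg differ by a factor of 4.35/1.57 = 2.8. Reversing the sign makes the model run, but the result no longer measures the effect in mmHg.

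**If negative values were dropped to force a fit.** The plan does not propose this. In the five rows the arm difference shrank from −2.48 to −0.89, −2.58 to −0.96, −3.96 to −0.35, 1.57 to 0.58 and 4.35 to 2.92 mmHg. It was attenuated each time and kept its direction.

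**The case against.** The strongest reply is that the plan already gives the right model. DBP change is continuous, so it gets the identity link unless someone declares it non-normal. The authors may have had counts in mind: encounter counts are neither categorical nor normal, and a Poisson model suits them. Analysts are blinded to allocation until the analyses are complete, which limits selective switching. A model that stops with an error is also a visible failure rather than a hidden bias.

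Most of this stands. It makes the problem conditional and limits the harm. It does not remove the problem, because the sentence sits among the rules for secondary outcomes, does not mention counts, and among the listed secondary endpoints can alter only the two blood pressure changes. Blinding does not make the model valid or fix the effect measure.

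A reader might infer more than the documents support:

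- *That the changes are mostly negative.* No distribution is given. Patients can qualify on SBP alone (Section 4.1), so the expected fall in DBP is unknown.
- *That the fallback is bound to be triggered with 49395 patients.* This would be likely under a formal normality test, but the plan names none.
- *That the arm difference would be reversed.* The plan does not say that negative values would be dropped, and dropping them in the simulations attenuated the difference without reversing it.
- *That the primary analysis is affected.* It has its own identity-link sentence and is not clearly covered by the fallback.

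**Conclusion.** Wrong as written, of minor severity. The fallback has neither a trigger nor a range restriction, and the listed secondary endpoints that it can move are signed scores for which a log-link Poisson model is unsuitable. The fit fails when arm means are negative; with the sign reversed it can run, but yields a ratio of mean changes.

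The argument needs only that the changes can be negative and that their mean can be zero or below; it does not need any particular share of negative values. It is conditional on an outcome being called non-normal. The numerical illustrations rest on assumed means, SDs and ICC, and on one software implementation. For the gap, it also rests on the contrast being estimated from a model of SBP change.

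**What to change.** Replace the fallback sentence in Section 9.3 with text to this effect:

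> The log-link Poisson GEE is used only for binary and count outcomes, such as numbers of encounters. Change in DBP and the SBP-gap contrast are analysed with an identity link and a Gaussian working model, whatever their distribution, with clinic-level robust variance and a small-sample correction for 24 clinics.

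The correction belongs in the text because robust variance relies on the number of clinics, not on the 49395 patients, and uncorrected it tends to be too small with 24. Once the Poisson model is tied to outcome type, non-normal no longer needs a definition. If robustness to skew is wanted, a rank-based or trimmed comparison of clinic means can be added as a sensitivity analysis.

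The cost is one or two sentences. Poisson models remain available for the percentages and the encounter counts, and no data collection changes.

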### **5.2 Randomization and blinding**

Clinics will be randomized to treatment arms in equal proportions. We will use clinic-based cluster randomization to minimize the possibility of contamination in study interventions between practices and clinic staff. For the randomization, we will use covariate constrained randomization in R software based on clinic characteristics to reduce potential imbalances between the clinics assigned to the treatment arms. The clinics/providers will not be blinded to which arm they were assigned to, as blinding in the context of an intervention that is intended to motivate action will be infeasible. Physicians randomized to usual care will not have any way of accessing the EHR interventions. Patients of physicians in the usual care arm will have access to the patient portal but will not be receiving any assistance from medical assistants or any of the after-visit activities. Moreover, only primary care physicians will be included (specialists will not receive any enhanced clinical decision support or report cards), and feasibility data suggest that there is minimal crossover of patients with other primary care physicians given the nature hypertension management at Advocate. Therefore, any risk of contamination within practices is low, and any contamination that does exist would bias the trial results towards the null.

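### Twenty-four clinics are allocated by constrained randomization, but the primary GEE leaves out the constraint variables and states no small-sample method, so its 5% level is not assured

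*Combined protocol and SAP*

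**What the plan says.** - **Allocation.** Section 5.2: "we will use covariate constrained randomization in R software based on clinic characteristics to reduce potential imbalances". Clinics are split equally, so the 24 clinics give 12 per arm.
- **Primary model.** Section 9.3: "we will use generalized estimating equations (GEE) to adjust for the cluster design with an identity link function and normally-distributed errors". No working correlation, variance estimator, small-sample correction, degrees of freedom or randomization test is given here or elsewhere in the text available.
- **Covariates.** The closing paragraph of section 9.3: "our primary analyses are planned as unadjusted; however, if there are strong patient-level predictors of the outcomes not balanced by stratified randomization". The sentence ends by committing to adjust for such predictors in the primary analysis itself.
- **Imbalance rule.** Earlier in section 9.3: "For baseline characteristics between arms with a standardized difference >0.1, we will repeat our analyses after adjusting for these covariates". This is a repeat of the analysis, not a change to the primary one.
- **Secondary outcomes.** Also GEE, "with a log-link function and Poisson-distributed errors for categorical variables", on the same 24 clinics.
- **Test level.** Section 9.2 assumes "an alpha threshold of 0.05, and an intra-cluster correlation (ICC) of 0.1".

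**The concern.** Constrained randomization admits only allocations in which the chosen clinic characteristics are close to balanced. If those characteristics predict the outcome, the treatment estimate varies less from one allowed allocation to another than it would under simple randomization. An unadjusted analysis does not know this: its standard error still includes the variance that balance has removed. The test becomes conservative and the intervals too wide.

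The second gap pulls the other way. With 12 clinics per arm, an uncorrected sandwich variance is biased downwards, and a normal reference ignores the error in estimating it.

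The false-positive rate for the primary outcome therefore depends on a software default and on how prognostic the constraint variables prove to be. Neither is settled in the plan, and the secondary GEEs leave the same points open. The design is also named differently in the two sections: constrained in 5.2, stratified in 9.3.

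**Working it through.** **Inputs (sections 5.2 and 9.2).** 24 clinics, 12 per arm; 49,395 patients; SD 13.5; ICC 0.1; difference 5.0 mmHg; alpha 0.05, taken as two-sided because the sidedness is not stated.

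**Step 1. Reproduce the plan's power.**
- Mean clinic size m = 49,395/24 = 2,058.1.
- Design effect = 1 + (m − 1) × 0.1 = 206.7.
- Effective n per arm = 24,697.5/206.7 = 119.5.
- SE = 13.5 × √(2/119.5) = 1.747, so 5.0/1.747 = 2.863.
- Power on a normal reference = Φ(2.863 − 1.960) = 81.7%, which agrees with the plan's "will provide >80% power to detect differences in our primary outcome". On t(22) it is 78.1%.

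**Step 2. Uncorrected sandwich, constraint variables not prognostic.** With equal clinics the exchangeable GEE reduces to a comparison of clinic means. The uncorrected sandwich variance is then (12 − 1)/12 of the unbiased one. The z test rejects when |t(22)| > 1.960 × √(11/12) = 1.877, which has probability 7.4%.

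**Step 3. Prognostic constraint variables left out.** Let the variables explain a share s of between-clinic variance and be balanced almost exactly. Between-clinic variance is 0.1 × 13.5² = 18.2. Sampling variance of a clinic mean is 0.9 × 13.5²/2,058 = 0.08. So almost all the variance of a clinic mean lies between clinics, and the true SE is roughly √(1 − s) times the one the unadjusted model reports. The rejection rate is about P(|t(22)| > c/√(1 − s)), with c = 1.877 uncorrected or c = 2.074 corrected.
- At s = 20%: 1.877/0.894 = 2.098 gives 4.8%; 2.074/0.894 = 2.319 gives 3.0%.
- At s = 50%: 1.877/0.707 = 2.654 gives 1.5%; 2.074/0.707 = 2.933 gives 0.8%.

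**Step 4. Simulation.** One covariate, best 10 of 100 candidate allocations, 60,000 trials per cell (160,000 for the permutation test, which used the best 200 of 2,000). KC is the Kauermann-Carroll corrected variance. Type I error, %:

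| Analysis | s = 0 | 10% | 20% | 50% |
|---|---|---|---|---|
| Unadjusted, uncorrected z | 7.6 | 6.0 | 4.7 | 1.3 |
| Unadjusted, KC with t(22) | 5.2 | 3.9 | 2.9 | 0.7 |
| Permutation over the allowed set | 5.0 | 5.0 | 5.0 | 5.1 |

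Over the same four shares, adjusted uncorrected z gives 8.0–8.3% and adjusted KC with t(21) gives 4.9–5.2%. With three covariates, adjusted uncorrected z gives 9.8–10.2% and adjusted KC with t(19) gives 5.0–5.3%.

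**Step 5. Interval width.** Mean 95% width, unadjusted t(22) against adjusted t(21): 7.16 against 7.18 mmHg at s = 0, and 7.19 against 6.42 at s = 20% (7.19/6.42 = 1.12).

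**Step 6. Other conditions.**
- Unequal clinics with exchangeable weights (assumed size CV 0.6 and 1.0, s = 0): unadjusted uncorrected z 7.4% and 7.3%; adjusted KC with t(21) 5.0% and 4.9%.
- An independence working correlation (CV 0.6, s = 0) moves unadjusted uncorrected z to about 9.5%.
- Secondary binary outcomes (log-Poisson, assumed rates 30–70%, ICC 0.02 or 0.1): unadjusted uncorrected z 6.9–7.5%, 4.0–5.0% and 1.3–1.6% at s = 0, 20% and 50%; adjusted KC with t(21) 4.2–5.2%.

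**The case against.** **The primary analysis is not simply unadjusted.** The plan commits to bringing strong, unbalanced patient-level predictors into it, and a constraint variable built from patient data could enter that way. This stands, but it is not a cure. The exception is patient-level and triggered by imbalance, whereas the constraint variables are clinic-level and balanced by design. It also makes the covariate set of the primary model depend on the observed data, a step that none of the calculations above includes. The fix therefore has to deal with that clause as well.

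**The 7.4% belongs to an analysis the plan does not name.** This also stands. A reader might infer that the trial's false-positive rate is inflated. The documents do not support that: the software may apply a correction, and prognostic constraint variables would pull the rate down. With one covariate explaining 10–20% of between-clinic variance, even the uncorrected test is at 6.0–4.7%.

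**Large precision losses rest on assumed shares.** They do. At an assumed 50% share the unadjusted interval is 42% wider (7.24 against 5.09 mmHg), but nothing in the documents supports that share. The endpoint is a change in blood pressure, which may already remove some persistent differences between clinics.

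**The power claim.** A reader might infer from 78.1% that the sample-size statement is wrong. It is not: it reproduces at 81.7% on a normal reference, and the gap is within rounding of the ICC (80.1% on t(22) at 0.095; 79.8% on the normal reference at 0.105).

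**The constraint variables may be named elsewhere.** Part of the document was not available to this review. The point does not depend on their being unnamed; it depends on their absence from the primary model.

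**Conclusion.** The concern holds as a mismatch between design and analysis together with an unspecified small-sample method. It should be fixed before analysis. It does not invalidate the trial.

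The omission and the direction of each effect are firm. The sizes are conditional. The 7.4% needs equal clinics, an uncorrected sandwich, a normal reference and constraint variables that are not prognostic. The 3% and the 12% need one covariate, tight balance and an assumed 20% share. Across the scenarios in the table, the unadjusted test rejects between about 1% and 8% under the null, depending on matters the plan leaves open.

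The two parts must be corrected together. A small-sample correction alone leaves a conservative test if the constraint variables matter; adjustment alone raises the error rate to about 8–10%.

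**What to change.** 1. In section 9.3, adjust the primary GEE for the clinic characteristics used in the constrained randomization, listed as a fixed, pre-specified set. State clinic as the cluster, an exchangeable working correlation, a small-sample corrected sandwich variance (for example Kauermann-Carroll) and a t reference on 22 df less one per clinic-level covariate. A permutation test over the allowed allocations is an acceptable alternative.
2. Apply the same approach to the secondary GEEs.
3. In the closing paragraph of section 9.3, remove the statement that the primary analysis is unadjusted and the reference to stratification, and name the design as section 5.2 does.
4. Move the imbalance-triggered patient-level adjustment into sensitivity analyses, beside the rule based on a standardized difference above 0.1, so that the primary covariate set does not depend on observed imbalance.

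The cost is SAP wording and standard software options. If the constraint variables are not prognostic, power is 78.0% with one covariate, 76.7% with three and 76.8% for the permutation test, against 78.1% unadjusted on t(22): a loss of at most 78.1 − 76.7 = 1.4 points. At an assumed 10% share, adjusted power is 82.2% with one covariate and 80.7% with three. Section 9.2 needs no change on this account.
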